4.3 Subject selection mode

4.3.1 Inclusion criteria

- Patients 18 years of age or older
- Admitted to the RVH and MGH intensive care units from February to October 2018
- Patients requiring mechanical ventilation and receiving continuous or regular intermittent opioids for at least 72 hours (calculated from the hour of administration of the first opioid dose)
 - o Recent prospective observational studies in the PICU and adult ICU populations have demonstrated that iatrogenic withdrawal symptoms may develop following 3-5 days of continuous opioid therapy (5, 8)
 - o Patient will be considered as receiving regular intermittent opioids if more than half of the scheduled "as-needed" doses within 24 hours were administered.
 - In the event that only prn narcotics are prescribed on a q1h prn or q2h prn basis, patients will be eligible if ≥ 4 prn doses are required per day.
- Weaning of at least 10% from previous stable opioid dose
 - o A weaning episode is defined as a $\geq 10\%$ decrease in the total stable opioid dose received over 4 hours for opioid infusions and over 12 hours for intermittent opioid administration (22)
 - o According to our previous experience (i.e. WAAICUP-1), the weaning definition of $\geq 10\%$ was chosen for practical reasons (8)

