5.1 Statistical analysis

5.1.1 Descriptive statistics

Demographic and clinical characteristics of patients who developed OIWS will be compared to those who did not. Categorical variables will be presented as proportions. For continuous variables, means and standard deviations will be computed for normal distributions whereas medians (interquartile range) will be used for non-normal distributions.

For the primary outcome, episodes will be compared between the withdrawal positive (W+) group and the withdrawal negative (W-) group. Every day on which the DSM-5 is positive is equivalent to an episode of withdrawal, whereas a negative DSM-5 counts as an episode in which no withdrawal was observed. Patients who are positive for at least one episode of withdrawal make up the W+ group, whereas those who did not have a single episode of withdrawal make up the W- group, thus eliminating crossover. If a single patient experiences multiple days of withdrawal, s/he will account for multiple episodes in the study. Signs and symptoms will be tallied per episode and compared between the two groups. The results will be presented as proportions (i.e. incidence of symptom per total episodes). In the event of a discordant inter-rater evaluation, only the positive result will be taken into account.

For the secondary outcome, serum cortisol levels and changes in serum cortisol levels are continuous variables and therefore descriptive statistics will be used as stated above, depending on the distribution.

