Cardiac symptoms	Hypertension	Highest Systolic blood pressure (mmHg) according to nurse assessment in the previous 24h	Quantitative continuous
		Highest MAP (mmHg) according to nurse assessment in the previous 24h	Quantitative continuous
	Tachycardia	Highest HR in the previous 24h	Quantitative continuous
		Lowest heart rate in previous 24h	Quantitative continuous
		Is patient on a beta-blocker ; Yes or No	Qualitative nominal (dichotomous)
Respiratory symptoms	Frequent suction	Number of times patient required endotracheal suctioning in the previous 24h according to nurse assessment	Quantitative continuous
	Lacrimation	Presence during evaluation or according to nurse assessment in the previous 24h	Qualitative nominal
	Rhinorrhea	Presence during evaluation or according to nurse assessment in the previous 24h	Qualitative nominal (dichotomous)
	Sneezing	Number of sneeze observed during evaluation or according to nurse assessment in the previous 24h	Quantitative continuous
		If more than 1 sneeze observed during evaluation or according to nurse assessment in the previous 24h	Qualitative nominal (dichotomous)
	Significant dyspnea	Highest respiratory rate (RR) recorded in the previous 24h according to nurse assessment	Quantitative continuous
		Lowest respiratory rate (RR) recorded in the previous 24h	Quantitative continuous

		according to nurse assessment	
Gastrointestinal symptoms	Diarrhea	Presence of ≥ 3 BMs (loose/watery stools), in past 24 hours according to nurse assessment	Qualitative nominal (dichotomous)
		Number of BM in the previous 24h according to nurse assessment	Quantitative continuous
		Rectal tube required (yes or no)	Qualitative nominal (dichotomous)
	Feeding intolerance (gastric residuals)	Present if nurse discontinued or decreased enteral feeding during previous 24h due to gastric residuals of more than 500 mL according to nurse assessment	Qualitative nominal (dichotomous)
	Nausea	Presence during previous 24h according to patient, nurse assessment or use of antiemetic medications such as dimenhydrinate and ondansetron (indication to validate with nurse when necessary)	Qualitative nominal (dichotomous)
Vomiting	Presence or absence of vomiting episode(s) or retching or gagging in the previous 24h according to nurse assessment	Qualitative nominal (dichotomous)	

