Appendix XII. Critical-Care Pain Observation Tool (CPOT) developed by Gelinas et al.

Indicator	Score	Checklist
Facial expression	Relaxed, neutral	0 No muscle tension observable  Eyes closed 
	Tense	1 Frowning/Brow lowering  Orbit tightening/Wincing  Levator contraction  Mouth opening  Eye opening  Eye weeping/tears  Eyebrow raising  Blinking 
	Grimacing	2 Frowning/Brow lowering  Eyes tightly closed  Levator contraction  Mouth opening  Biting endotracheal tube/Clenched teeth  Flushing 
Body movements	Absence of movements or normal position	0 Does not move at all  Normal position 
	Protection	1 Slow, cautious movements  Limb flexion  Trying to reach pain site/tubes  Touching pain site/Guarding  Seeking attention  Rubbing/Massaging pain site  Shaking  Withdrawing  Decortication  Decerebration 
	Restlessness/Agitation	2 Touching/Pulling tubes  Fidgeting/Restlessness  Arching  Pushing  Striking at staff/Defensive grabbing  Attempting to sit up  Trying to climb out of bed 
Compliance with the ventilator (intubated patients)	Tolerating ventilator or movement	0 Alarms not activated, easy ventilation 
	Coughing but tolerating	1 Alarms activated, stop spontaneously  Coughing  Gag reflex 
	Fighting ventilator	2 Asynchrony  Blocking ventilation 
Vocalization (extubated patients)	Talking in normal tone or no sound	0 No sound  Normal tone 

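### Feeding intolerance and suctioning are set against all episodes although they need feeding or an airway tube, and gagging is scored as vomiting, so three signs may be distorted or diluted

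*Combined protocol and SAP*

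**What the plan says.** Section 5.1.1 makes the sign comparison the primary outcome. Each DSM-5 evaluation day is an episode, and "Signs and symptoms will be tallied per episode and compared between the two groups". The denominator is then fixed: "The results will be presented as proportions (i.e. incidence of symptom per total episodes". No restriction to days on which a sign could occur is given, nor any code for a sign that could not apply.

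Appendix III defines the three signs at issue as follows:

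- Frequent suction: "Number of times patient required endotracheal suctioning in the previous 24h according to nurse assessment". It is typed as a continuous quantity, with no cut-off for what counts as frequent.
- Feeding intolerance: "Present if nurse discontinued or decreased enteral feeding during previous 24h due to gastric residuals of more than 500 mL". It is dichotomous.
- Vomiting: "Presence or absence of vomiting episode(s) or retching or gagging in the previous 24h according to nurse assessment". It is dichotomous, and the cause of the gagging is not considered.

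Section 4.3.1 admits "Patients requiring mechanical ventilation and receiving continuous or regular intermittent opioids for at least 72 hours", so every patient is ventilated at entry. Section 4.5 runs daily evaluations to the day of ward transfer, or to 14 days after the first wean for those still in the ICU. One ward evaluation follows 24 to 96 hours after transfer. Extubation does not end evaluation, and the pain tool in Appendix XII has a row for extubated patients.

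Section 4.4.1 collects the total duration of ventilation, and notes enteral feeds only as a confounder of diarrhea. No daily airway-tube variable is listed, and neither item enters the sign comparison.

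**The concern.** Two separate mechanisms are at work.

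**Denominator.** On an episode without enteral feeding, feeding intolerance cannot be present. On an episode without an airway tube, the suction count can only be zero. Dividing by all episodes counts these as absences. If W+ and W- episodes differ in how often patients were fed or tubed, the two groups will differ on these signs for that reason alone, or a real difference will be masked.

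**Composite item.** Gagging can come from the tube as well as from nausea. The plan's own pain tool lists the gag reflex under ventilator compliance for intubated patients, at the level "Coughing but tolerating". Folding it into vomiting adds a background rate that can swamp the vomiting signal.

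At stake is the descriptive sign profile that Section 4.1 says is a step toward a bedside screening tool. Section 2 reports that vomiting did not correlate with withdrawal in an earlier adult study. A composite dominated by gagging would be a poor test of that result.

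**Working it through.** The plan states no sign rate, tube share, feeding share or power for this comparison, so there is no figure to reproduce. All rates below are assumptions, used to show the range.

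**Step 1: denominator, no true effect.** Let *t* be the share of a group's episodes on which the sign could occur, and *r* the sign rate on those episodes. The planned proportion is *t* × *r*; the at-risk proportion is *r*. Set *r* = 30% in both groups.

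| *t* in W+ v W- | Planned proportions | Ratio |
|---|---|---|
| 50% v 50% | 15% v 15% | 1.0 |
| 80% v 40% | 24% v 12% | 2.0 |
| 40% v 80% | 12% v 24% | 0.5 |

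With *t* between 30% and 90% and *r* between 10% and 50%, the spurious difference runs from -30 to +30 points: 0.50 × (0.90 - 0.30) = 0.30. It is zero whenever the shares are equal.

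**Step 2: denominator, true effect.** Set *r* = 40% in W+ and 20% in W-, a 20-point difference and a ratio of 2.0.

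| *t* in W+ v W- | Planned proportions | Difference | Ratio |
|---|---|---|---|
| 80% v 80% | 32% v 16% | +16 | 2.0 |
| 50% v 50% | 20% v 10% | +10 | 2.0 |
| 30% v 30% | 12% v 6% | +6 | 2.0 |
| 40% v 80% | 16% v 16% | 0 | 1.0 |
| 30% v 90% | 12% v 18% | -6 | 0.67 |

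Equal shares shrink the difference but keep the ratio. Unequal shares can hide or reverse the effect. An at-risk denominator returns 40% v 20% in every row.

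**Step 3: suctioning.** As a count with no threshold it has no proportion over total episodes. Its problem is different: zeros that only reflect the absence of a tube are mixed with zeros from tubed patients who needed no suction, and Appendix III gives no rule for turning the count into a sign.

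**Step 4: vomiting composite.** Let *v* be the true vomiting rate and *G* the share of days with gagging, taken as independent. The item reads 1 - (1 - *v*)(1 - *G*). Take *v* = 15% v 5%, a true ratio of 3.0, and the same *G* in both groups.

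- *G* = 10% (for example, half of days tubed and gagging on 20% of those): 1 - 0.85 × 0.90 = 23.5% v 1 - 0.95 × 0.90 = 14.5%; ratio 1.6.
- *G* = 32% (80% tubed, gagging on 40% of those): 1 - 0.85 × 0.68 = 42.2% v 1 - 0.95 × 0.68 = 35.4%; ratio 1.2.
- *G* = 50%: 1 - 0.85 × 0.50 = 57.5% v 1 - 0.95 × 0.50 = 52.5%; ratio 1.1.

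So the composite loses contrast even when tube status is balanced. If tube status is unbalanced it can also create a contrast. With true vomiting of 5% in both groups, gagging on 20% of tubed days, and tube shares of 80% v 40%, it reads 1 - 0.95 × 0.84 = 20.2% v 1 - 0.95 × 0.92 = 12.6%.

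**The case against.** The strongest reply is that the denominator problem needs tube or feeding status to differ between W+ and W- episodes, and no figure in the documents shows this. Both groups are evaluated after a wean and under the same follow-up rule, so waking and extubation occur in both. This stands: Step 1 gives zero bias at equal shares. The Introduction and Section 4.4.1 do link withdrawal to longer ventilation, which makes a difference plausible, but neither gives its direction or size at the level of episodes.

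Other points carry weight:

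- The data collection sheets are not in the documents and may already separate 'not applicable' from 'absent'. Section 5.1.1 would still need to say so.
- The documents do not say how often gagging is provoked by the tube, or that nurses would report it under vomiting. The tube cause is an inference.
- Gagging during care procedures may not be separable in 24-hour nurse reports, so a rule that excludes it by context could be unworkable.
- The proportion over all episodes is a legitimate description for a bedside tool. If withdrawal itself prolongs ventilation, restricting to tubed days conditions on a possible consequence of withdrawal. This argues for showing both figures.
- Section 6.2 acknowledges confounding and calls the analysis predominantly descriptive, and no test is planned on the signs. Description is still misleading if the denominator is wrong.

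A reader might go further and infer that these signs follow tube status instead of withdrawal, or that they are sure to enter a future tool. The documents support neither. Within fed or tubed days the signs can still reflect withdrawal, and no rule for carrying signs forward is stated.

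**Conclusion.** The point holds in a limited form. By their own definitions, feeding intolerance and endotracheal suctioning cannot be recorded without enteral feeding or an airway tube, while the stated denominator takes in extubated, unfed and ward episodes. They are confounded by tube or feeding status if that status differs between W+ and W- episodes. The direction and size are unknown, and there is no spurious contrast if shares are equal. For suctioning there is the further gap that no proportion is defined.

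The vomiting item is a separate weakness that does not depend on unequal tube shares. Under the assumed rates a threefold contrast falls to a ratio between 1.6 and 1.1. This rests on gagging being reasonably common and independent of vomiting; if gagging is rarely recorded, the loss is small.

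The matter affects three signs among many in Appendix III. It is worth correcting because the sign comparison is the primary outcome and the change is small.

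**What to change.** 1. On the daily sheet, record airway-tube status (endotracheal or tracheostomy) and enteral-feeding status at each evaluation, including the ward visit. Enteral feeds are already read from the flow sheet for the diarrhea confounder.
2. In Section 5.1.1, report feeding intolerance over enterally fed episodes, with 'not applicable' coded separately from 'absent'. The all-episode proportion may be shown alongside.
3. Summarise suctioning as a count over episodes with an airway tube.
4. In Appendix III, make vomiting one row and retching or gagging another, and note tube status for the second.

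The cost is smaller denominators for two signs and slightly more daily recording. Tube and feeding status is best captured prospectively, since the day-by-day record may be hard to rebuild later.

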- **Presence of agitation due to a condition other than OIWS** (qualitative nominal - dichotomous) (10)
 - During ICU stay: according to the Richmond Agitation-Sedation Scale (RASS) as measured by investigators and/or nursing staff, collected daily once opioid weaning is initiated (qualitative ordinal) and until transfer
 - After transfer to ward: according to the Agitated Behavior Scale (ABS), measured once by investigators within 24-96 hours of transfer (qualitative ordinal)
- **Presence of pain** (qualitative nominal - dichotomous)
 - In patients unable to self-report: Critical-Care Pain Observation Tool (CPOT) score > 2, as measured by investigator or medical staff, collected daily once opioid weaning is initiated
 - In patients able to self-report: Numeric Rating Scale (NRS) ≥ 4, collected daily once opioid weaning is initiated
 - The symptoms of uncontrolled pain may confound OIWS assessment (20)

- **Administration of co-analgesia during ICU hospitalization** (e.g. acetaminophen, non-steroidal anti-inflammatory drugs, anticonvulsants, antidepressants, corticosteroids) (qualitative nominal)
 - Agent and total daily dose will be noted daily according to MAR
 - Co-analgesia is used to treat or attenuate pain, which may confound OIWS assessment
 - Anti-inflammatory drugs also act as antipyretics, which may confound OIWS assessment
- **Presence of nicotine replacement therapy during ICU admission** (qualitative nominal - dichotomous)
 - Nicotine consumption in mg (qualitative continuous) prior to ICU admission (e.g. cigarettes, nicotine replacement therapy) and whether nicotine replacement therapy was prescribed in ICU will be noted according to medication reconciliation chart at admission (qualitative nominal)
 - Nicotine withdrawal or nicotine-induced delirium may confound OIWS assessment (45)
- **Factors which may confound specific signs and symptoms of OIWS** (qualitative nominal - dichotomous)
 - Fever secondary to documented or suspected infection
 - According to diagnosis documented in medical chart
 - Diarrhea due to *Clostridium difficile* infection or enteral feeds
 - According to positive *C. difficile* antigen detection test in medical chart or presence of enteral feeds in patient flow sheet
- **Use of physical restraints** (qualitative nominal - dichotomous) (52)
 - Collected daily according to medical chart
 - Patients with restraints are more likely to be given supplemental sedative and analgesic agents which may confound OIWS assessment

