Once the patient begins the targeted opioid weaning of $\geq 10\%$, investigators will perform evaluations daily between 10am and 2pm. These evaluations will consist of using pre-tested data collection sheets to record signs and symptoms of possible OIWS, opioid doses, administered medications, laboratory values and other clinical data such as the RASS, CPOT and CAM-ICU scores. Data collection will be based on subject observation and interview when possible, nurse assessments, medical charts and laboratory results. Serum cortisol levels will be measured on the first day of opioid weaning (± 2 hours from dose decrease) and on the day patient is transferred to the ward or 72 hours from start of weaning whichever occurs first.

Once a weaning episode is identified, the physician collaborator will be contacted to perform daily DSM-5 evaluations. DSM-5 evaluations will be placed in opaque envelopes and investigators will be blinded to the results throughout the study. Additionally, for each patient, at least one inter-rater DSM-5 evaluation between 2 physician collaborators will be performed in order to assess interrater reliability. The two evaluations will be done within 2 hours of each other to minimize time-related discrepancies.

If opioid weaning is unsuccessful and opioid dose is re-increased, the subject will continue to be observed, however daily evaluations will only resume at the next weaning episode. Daily follow-up ends on day of transfer to the ward. One additional data collection and DSM-5 evaluation will be performed on the same day within 24 to 96 hours following transfer. Follow up ends 14 days after initial opioid weaning if patient remains in the ICU or if patient dies.

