Dermatologic symptoms	Mottling	Presence of violaceous marbled discoloration of the skin during evaluation or according to nurse assessment in the previous 24h	Qualitative nominal (dichotomous)
	Piloerection	Presence during evaluation or according to nurse assessment in the previous 24h	Qualitative nominal (dichotomous)
	Sweating	Presence without apparent reason (not caused by room temperature) during evaluation or according to nurse assessment in the previous 24h	Qualitative nominal (dichotomous)
Musculoskeletal symptoms	Bone, joint or muscle aches	Presence during evaluation or according to nurse assessment in the previous 24h	Qualitative nominal (dichotomous)
	Muscle cramps	Presence during evaluation or according to nurse assessment in the previous 24h	Qualitative nominal (dichotomous)
	Muscle tone	Presence during evaluation or according to nurse assessment in the previous 24h	Qualitative nominal (dichotomous)

		(e.g. clenching wrists and toes, hunched shoulders, abnormal tense position of head, arm or legs)	
	Uncoordinated/ repetitive movement	Presence of involuntary movements of arm and/or legs, muscle twitches, during evaluation or according to nurse assessment in the previous 24h	Qualitative nominal (dichotomous)

^a Previous 24h designate the interval between midnight of the previous day and midnight of the day on which evaluation of the signs and symptoms occurs. A fixed time frame was chosen to standardize collection of signs and symptoms.

^b Nurse assessment comprises written (i.e. notes in medical chart or patient flow sheet) and/or verbal communication.

^c On the day of transfer, patients will be evaluated from midnight of the previous day until time of evaluation. Following transfer to ward, patients will be evaluated from midnight of the current day to time of evaluation.

Appendix IV. Diagnostic and Statistical Manual of Mental Diagnosis-V (DSM-5): “Opioid Withdrawal” criteria.

Diagnostic criteria:

A. Presence of either of the following;

1. Cessation of (or reduction in) opioid use that has been heavy and prolonged (i.e., several weeks or longer).
2. Administration of an opioid antagonist after a period of opioid use.

B. Three (or more) of the following developing within minutes to several days after

1. Dysphoric mood.
2. Nausea or vomiting.
3. Muscle aches.
4. Lacrimation or rhinorrhea.
5. Pupillary dilation, piloerection, or sweating.
6. Yawning.
7. Fever.
8. Insomnia.

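### Section 5.1.1 keeps days without self-report in the denominator for symptoms that rely largely on it, chiefly aches and cramps, so these may be undercounted and their group contrast may be distorted

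*Combined protocol and SAP*

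**What the plan says.** Section 5.1.1 makes the evaluation day the unit of analysis: "Every day on which the DSM-5 is positive is equivalent to an episode of withdrawal", and a day with a negative DSM-5 counts as an episode without withdrawal. For every symptom, "The results will be presented as proportions (i.e. incidence of symptom per total episodes". No section gives a code for a symptom that could not be assessed, or a rule for a day without self-report.

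The plan expects such days. Section 4.3.1 enrols "Patients requiring mechanical ventilation and receiving continuous or regular intermittent opioids for at least 72 hours". Section 4.5 states: "Data collection will be based on subject observation and interview when possible, nurse assessments, medical charts and laboratory results". For pain, section 4.4.1 changes the instrument by ability to self-report: "In patients unable to self-report: Critical-Care Pain Observation Tool (CPOT) score > 2, as measured by investigator or medical staff", and an NRS of 4 or more in patients who can. No other symptom is treated this way.

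Appendix III sets the sources for the subjective symptoms:
- "Bone, joint or muscle aches" and muscle cramps: presence at the evaluation or by nurse assessment, recorded yes/no.
- Nausea: patient, nurse, or antiemetic use.
- Anxiety: patient or nurse.
- Hallucinations: apparent behaviour, by patient or nurse.
- Dysphoria: the physician's DSM-5 evaluation.

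A nurse assessment may be written or verbal (Appendix III, note b). A DSM-5 diagnosis needs at least three of eight criterion B items, which include dysphoric mood, nausea or vomiting, and muscle aches (Appendix IV).

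**The concern.** A patient who is sedated, intubated or delirious can be examined for sweating or tremor but may be unable to report a cramp. If nobody else records it, the day adds to the denominator and not to the numerator, which has the same effect as a true absence. The symptom's frequency is then understated.

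The group contrast can be affected too. A patient who can self-report has more criterion B items on which to reach three, so DSM-5-positive days may contain more self-report days than negative days do. A symptom unrelated to withdrawal could then look more frequent in withdrawal simply because it was easier to record. The primary objective is to find signs and symptoms specific to OIWS, and section 4.1 looks ahead to a bedside screening tool, so these proportions are the main result.

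**Working it through.** **No plan figure to reproduce.** Section 5.2 sets 50 patients on feasibility (88 eligible, around 50 consenting). The documents give no symptom rates, no share of days with self-report and no proxy detection rate. All inputs below are therefore assumptions.

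**Inputs.**
- c: share of days with self-report. Base 50%, range 30% to 70%.
- p: prevalence of each criterion B item, items independent. Base 20%, range 15% to 30%.
- q: true prevalence of a symptom unrelated to OIWS and outside the DSM-5 list, such as cramps. Set at 40% of days.
- d: share of true symptoms that a proxy records on days without self-report. 0% to 80%.
- Criteria A, C and D are ignored. The comparison is of positive with negative days.

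**Step 1: level.** Recorded proportion = q × [c + (1 − c) × d], so the relative understatement is (1 − c) × (1 − d). At c = 50%:
- d = 0: 0.5 × 1 = 50%
- d = 25%: 0.5 × 0.75 = 37.5%
- d = 50%: 0.5 × 0.5 = 25%
- d = 80%: 0.5 × 0.2 = 10%

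With no proxy detection it is 70% at c = 30% and 30% at c = 70%.

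**Step 2: chance of a positive DSM-5.** On self-report days, A = P(at least 3 of 8 items) = 0.203 at p = 20%. On other days, dysphoria and aches are taken as depending on self-report and have prevalence p × d, with six items at p. Call that probability B.

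**Step 3: share of self-report days.** Among positive days, s+ = cA / [cA + (1 − c)B]. Among negative days, s− = c(1 − A) / [c(1 − A) + (1 − c)(1 − B)]. At d = 0, s+ = 0.203 / (0.203 + 0.099) = 0.67 and s− = 0.797 / (0.797 + 0.901) = 0.47.

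**Step 4: spurious gap.** Recorded proportion = q × [s + (1 − s) × d] in each set of days, so the gap is q × (1 − d) × (s+ − s−).

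| d | B | s+ | s− | Recorded, positive | Recorded, negative | Gap (points) |
|---|---|---|---|---|---|---|
| 0 | 0.099 | 0.67 | 0.47 | 26.9% | 18.8% | 8.1 |
| 25% | 0.124 | 0.62 | 0.48 | 28.6% | 24.3% | 4.3 |
| 50% | 0.150 | 0.58 | 0.48 | 31.5% | 29.7% | 1.8 |
| 80% | 0.181 | 0.53 | 0.49 | 36.2% | 35.9% | 0.3 |

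At 30% detection the gap is about 3.8. Over c from 30% to 70% and p from 15% to 30%, it runs from about 6 to 8 points at d = 0 and from about 1.5 to 2 points at d = 50%. It scales in proportion to q.

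**Step 5: direction.** Now set the self-report shares directly, with a true prevalence of 30% in both groups and d = 0:
- 80% of W+ days and 40% of W- days: 24% v 12%
- 50% and 50%: 15% v 15%
- 40% and 70%: 12% v 21%

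The undercount arises in all three cases. The contrast is biased only when the shares differ, and its sign follows theirs.

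**Step 6: what a new denominator cannot do.** Aches are a criterion B item. On self-report days alone, at p = 20%, aches appear on 41.7% of positive and 14.5% of negative days, a ratio of 2.9 (2.5 at p = 30%), with no relation to withdrawal built in. That comes from their use in the diagnosis.

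**The case against.** The strongest reply is that Appendix III makes none of these symptoms patient-report-only. Each has another route: nurse, observed behaviour, antiemetic use, or the physician's DSM-5 evaluation. This stands. A reader might infer that six symptoms can come only from the patient; the appendix contradicts that. It leaves aches and cramps as the main cases, because no behavioural or drug proxy is named for them, with nausea and anxiety behind.

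Second, the documents nowhere say that a day without self-report is scored as absent, and the collection sheets are not reproduced. That is fair as to coding. The stated denominator still keeps such a day in, and a symptom nobody recorded cannot enter the tally.

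Third, the direction of the contrast is inferred from the three-of-eight rule. No figure on DSM-5 positivity by ability to communicate is given, and W+ and W- are defined by patient, so a day-level illustration carries over only if self-report ability tends to persist within a patient. This also stands.

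Fourth, a larger gap of 9 to 14 points can be obtained, but only with zero proxy detection and with the nausea-or-vomiting item lost as well. Vomiting is recorded by nurse assessment, so the documents do not support that case.

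Finally, section 6.2 calls the analysis mainly descriptive and disclaims significance. That limits the inference drawn from the proportions, but it does not excuse an unsuitable denominator for them.

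**Conclusion.** The point holds in a limited form. The all-episode denominator will understate aches and cramps, and to a lesser degree nausea and anxiety, by however much proxies miss. With half of days self-report days, that is 50% with no proxy detection and 10% at 80% detection.

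Distortion of the W+ versus W- contrast is possible rather than shown. Under the assumptions above it is about 8 points at worst in the base case, about 4 at 25% to 30% detection, about 2 at 50%, and under 1 at 80%. A reader might conclude that the plan is bound to make these symptoms look specific to OIWS. The documents do not support that: they give neither self-report shares by group nor proxy detection rates, and the bias vanishes with equal shares and reverses if self-report is commoner on W- days.

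The change is worth making because the affected proportions belong to the primary outcome and the data needed are largely collected already.

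**What to change.** In section 5.1.1, flag each evaluation day by whether the patient gave a self-report, taken as an NRS having been obtained at that day's evaluation. A CPOT may exist on the same day, so the flag should rest on the presence of an NRS. It should be recorded at the ward visit too.

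- For aches and cramps, report the proportion over self-report days beside the all-episode proportion.
- For nausea and anxiety, do the same as a sensitivity analysis.
- Give the number of self-report days in W+ and W-, so that readers can see whether ability to self-report differs.
- Keep positives recorded by nurse, physician or antiemetic use on other days in the all-episode proportion. Replacing that denominator outright would discard valid observations.
- Leave hallucinations and dysphoria on the all-episode denominator.

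The cost is a few sentences, one derived flag, and fewer days behind a handful of proportions. The flag is imperfect, because the NRS reflects one moment while nurse-assessed symptoms cover a 24-hour window. The change does not touch the separate problem that aches and nausea are themselves DSM-5 criteria, and the report should say so.
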